7.4. Analysis of Other Efficacy Parameters

[figure not shown]
Proportion of participants who achieve BOR of CR, proportion of participants who achieve BOR of CR or PR, proportion of participants who achieve BOR of CCyR, and proportion of participants who achieve BOR of PCyR as assessed by central review committee will be summarized along with their 95% CI.

Duration of CR, DOR, and progression-free survival as assessed by central review committee will be analyzed by the Kaplan-Meier method.

For participants who have undergone stem cell transplant after treatment with pemigatinib without disease progression, transplant outcome data will be collected, including rates of graft failure, transplant-related mortality, graft-versus-host disease, and OS. Those data will be summarized (if there are sufficient number of participants who have undergone stem cell transplant, eg, > 10 participants) and listed.

Eastern Cooperative Oncology Group performance status at scheduled assessment times will be summarized.

7.5. Analysis of Exploratory Efficacy Variables

For all other scales, the standardized score will be calculated by the following:

$$\left(\frac{\text{RawScore} - 1}{\text{Range}} \right) \times 100$$

7.5.3. Other Exploratory Variables

8. SAFETY AND TOLERABILITY

[Appendix C](#) provides a list of data displays.

8.1. General Considerations

Summary tables may be replaced with listings when appropriate. For instance, an AE frequency table may be replaced with a listing if it only contains a few unique PTs reported on relatively few participants.

Unless otherwise stated, table summaries will be limited to TEAEs.

8.2. Adverse Events

8.2.1. Adverse Event Definitions

A TEAE is any AE either reported for the first time or worsening of a pre-existing event after the first dose of study drug and within 30 days of the last dose of study drug. Analysis of AEs (as discussed below) will be limited to TEAEs, but data listings will include all AEs regardless of their timing and in relation to study drug administration.

Adverse events will be tabulated by MedDRA PT and SOC. Severity of AEs will be graded using the NCI CTCAE v4.03. The CTCAE reporting guidelines and grading details are available on the Cancer Therapy Evaluation Program website.

A grading (severity) scale is provided for each AE term. If the toxicity is not included in the CTCAE v4.03 criteria, it will be rated on a scale of 1 to 4 as follows: 1 = mild, 2 = moderate, 3 = severe and 4 = life-threatening. The CTCAE v4.03 severity of Grade 5 will not be used; AEs resulting in death will be graded accordingly using Grades 1 through 4 and have the outcome noted as fatal. When the intensity of an AE changes over time for a reporting period (eg, between visits), each change in intensity will be reported as an AE until the event resolves.

The subset of AEs considered by the investigator to be related to study drug will be considered to be treatment-related AEs. The incidence of AEs and treatment-related AEs will be tabulated. Serious TEAEs will also be tabulated.

Any missing data pertaining to date of onset, causality, or severity must be queried for resolution. Unresolved missing causality and severity will be handled according to the following rules:

- An unresolved missing causality will be considered treatment-related.
- An unresolved missing severity will be identified as an unknown severity.

For purposes of analysis, all AEs will be considered TEAEs unless the AE can unequivocally be defined as not treatment-emergent.

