- Current evidence of clinically significant corneal disorder/keratopathy (including but not limited to bullous/band keratopathy, corneal abrasion, inflammation/ulceration, and keratoconjunctivitis, etc) or retinal disorder (including but not limited to macular/retinal degeneration, diabetic retinopathy, retinal detachment, etc) as confirmed by ophthalmologic examination.
- Use of any potent cytochrome P450 3A4 inhibitors or inducers within 14 days or 5 half-lives (whichever is shorter) before the first dose of study drug.

Pemigatinib, Dosage, and Mode of Administration:

Pemigatinib will be self-administered as a QD oral treatment on a 2-weeks-on-therapy and 1-week-off-therapy schedule or continuous administration (no planned dose hold). Each dose of pemigatinib should be taken as soon as possible after rising with or without food. Tablets will be available in strengths of █ mg and 4.5 mg. The starting dose will be 13.5 mg. One cycle will be defined as 21 days of treatment.

Reference Therapy, Dosage, and Mode of Administration:

Not applicable.

Study Schedule/Procedures:

Subjects will have regularly scheduled study visits at the clinical site as part of a 21-day cycle. Study visits are as follows:

- Screening: Day -28 through Day -1
- Cycle 1: Days 1, 8, and 15 (\pm 3 days)
- Cycles 2+: Day 1 (\pm 3 days) of each cycle or Day 1 (\pm 3 days) of every third cycle (with telemedicine visits conducted in between) when subject has reached the long-term treatment visit schedule (after completing Cycle 18).
- End of treatment (EOT): Upon permanently discontinuing study drug
- Safety follow-up: 30 days (+ 5 days) from date of last dose
- Disease status: Follow subject per standard of care until documented progression
- Survival follow-up: Every 12 (+2) weeks

Laboratory Tests:

Study visits will include sample collection for chemistry, hematology, coagulation, lipid panel, endocrine monitoring, and urinalysis testing. As of Protocol Amendment 6, lipid panel will only be analyzed at Cycle 1 Day 1. Additionally, hepatitis screening (serology) will be done at screening, and pregnancy testing will be done at screening, Day 1 of every cycle before dose administration, and EOT. Subjects who underwent hematopoietic stem cell transplant during the study will continue to have hematology blood tests done concomitantly with the bone marrow assessments.

Central Laboratory:

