5.4.5. Criteria for Permanent Discontinuation of Study Drug

The occurrence of unacceptable toxicity not caused by the underlying malignancy will be presumed to be related to study drug treatment and will require that the study drug be permanently discontinued. Unacceptable toxicity is defined as follows:

- Occurrence of an AE that is related to treatment with the study drug that, in the judgment of the investigator or the sponsor's medical monitor, compromises the subject's ability to continue study-specific procedures or is considered to not be in the subject's best interest.
- An AE requiring more than 2 dose reductions. Note: Reducing down to original dose following up-titration does not count toward the number of allowed dose reductions.
- Persistent AE requiring a delay of therapy for more than 21 days unless a greater delay has been approved by the sponsor.

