6.4. Follow-Up

6.4.1. Safety Follow-Up

The safety follow-up period is the interval between the EOT visit and the scheduled follow-up visit, which should occur 30 to 35 days after the EOT visit (or after the last dose of study drug if the EOT visit was not performed). Adverse events and SAEs must be reported up until at least 30 days after the last dose of study drug, the date of the follow-up visit, or until toxicities resolve, return to baseline, or are deemed irreversible, whichever is longer. Reasonable efforts should be made to have the subject return for the follow-up visit and report any AEs that may occur during this period.

If a subject is scheduled to begin a new antineoplastic therapy before the end of the 30-day safety follow-up period, then the safety follow-up visit should be performed before new antineoplastic therapy is started. Once new antineoplastic therapy has been initiated, the subject will move into the survival follow-up period.

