8.3.2. Reporting

Every SAE, regardless of suspected causality (eg, relationship to study drug(s) or study procedure or disease progression), occurring after the subject has signed the ICF through the last study visit (or 30 days after the last dose of study drug, whichever is later) must be reported to the sponsor (or designee) within **24 hours** of learning of its occurrence, unless otherwise specified by the Protocol. Any SAEs occurring more than 30 days after the last dose of study drug should be reported to the sponsor or its designee only if the investigator suspects a causal relationship to the study drug.

Information about all SAEs is collected and recorded on the Adverse Event form of the eCRF. The investigator must assess and record the causal relationship of each SAE to the study treatment.

The investigator must also complete the Incyte Serious Adverse Event Report Form, in English, and send the completed and signed form to the sponsor or designee within 24 hours of becoming aware of the SAE. The investigator must provide a causality assessment, that is, assess whether there is at least a reasonable possibility that the SAE is related to the study treatment: suspected (yes) or not suspected (no). Refer to the Incyte Reference Guide for Completing the Serious Adverse Event Report Form.

The contact information of the sponsor's study-specific representatives is listed in the investigator manual provided to each site. The original copy of the SAE Report Form and the confirmation sheet must be kept at the study site.

Investigational site personnel must report any new information regarding the SAE within 24 hours of becoming aware of the information in the same manner that the initial SAE Report Form was sent. Follow-up information is recorded on an amended or new SAE Report Form, with an indication that it is follow-up to the previously reported SAE and the date of the original report. The follow-up report should include information that was not provided on the previous SAE Report Form, such as the outcome of the event (eg, resolved or ongoing), treatment provided, action taken with study drug because of the SAE (eg, dose reduced, interrupted, or discontinued), or subject disposition (eg, continued or withdrew from study participation). Each recurrence, complication, or progression of the original event should be reported as follow-up to that event, regardless of when it occurs.

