9.4.2. Safety Analyses

9.4.2.1. Adverse Events

A TEAE is any AE either reported for the first time or worsening of a pre-existing event after the first dose of study drug. Analysis of AEs will be limited to TEAEs, but data listings will include all AEs regardless of their timing to study drug administration. Adverse events will be tabulated by the MedDRA preferred term and system organ class. Severity of AEs will be based on the NCI CTCAE v4.03 ([NCI 2010](#)) using Grades 1 through 4.

The subset of AEs considered by the investigator to have a relationship to study drug will be considered to be treatment-related AEs. If the investigator does not specify the relationship of the AE to study drug, then the AE will be considered treatment-related. The incidence of AEs and treatment-related AEs will be tabulated.

Subjects taking pemigatinib may develop HP, which is a known effect of selective FGFR inhibitors. The number and percentage of subjects with at least 1 event of HP will be tabulated.

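### SAP 8.2.1 adds an undeclared 30-day end to the TEAE window, so adverse events that start or worsen later, including related ones, are listed but enter no AE summary table

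*SAP*

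**What the plan says.** - **TEAE definition.** Protocol 9.4.2.1 gives a start and no end: "A TEAE is any AE either reported for the first time or worsening of a pre-existing event after the first dose of study drug". SAP 8.2.1 begins the same way and then bounds the period: "after the first dose of study drug and within 30 days of the last dose of study drug". SAP 9.1 records one departure from the Protocol, the efficacy evaluable population. The TEAE window is not listed.
- **What is tabulated.** SAP 8.1 restricts tables to TEAEs by default, and each AE summary in SAP 8.2.3 is a TEAE summary, including the related, serious and fatal ones. SAP 8.2.1 keeps all AEs in the listings whatever their timing, and treats an AE as a TEAE unless it clearly is not one.
- **What is collected.** Protocol 6.4.1 sets the collection period for serious and nonserious events alike: these "must be reported up until at least 30 days after the last dose of study drug, the date of the follow-up visit", with a further extension while a toxicity is neither settled nor judged irreversible; the longest of these periods applies. Protocol 8.3.2 requires every SAE to be reported "through the last study visit (or 30 days after the last dose of study drug, whichever is later"). It then limits SAEs more than 30 days after the last dose to those the investigator suspects are drug-related.
- **When the safety visit falls.** Protocol 6.4.1 describes a visit "which should occur 30 to 35 days after the EOT visit", and Tables 4 and 5 also count from EOT. The synopsis schedule reads "Safety follow-up: 30 days (+ 5 days) from date of last dose", and the synopsis paragraph on duration of participation also counts from the last dose.

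**The concern.** The analysis window is shorter than the collection period, and nothing in the SAP says that this was intended. The Protocol asks sites to look for and report events after day 30, and asks specifically for the serious ones thought to be caused by the drug. The SAP then removes those events from every incidence table. In a single-arm study the AE tables are the main quantitative account of safety. A reader of the clinical study report who knows only the Protocol definition would assume that late related events are in the related, serious and fatal counts.

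The length of the gap also depends on which Protocol passage a site follows for the safety visit, because the two anchors differ by the time between last dose and EOT. That time can be appreciable when treatment ends after a toxicity hold. One discontinuation criterion in Protocol 5.4.5 is: "Persistent AE requiring a delay of therapy for more than 21 days unless a greater delay has been approved by the sponsor".

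**Working it through.** The plan gives no figure on this point, so there is none to reproduce. The check is day arithmetic followed by tracing example events through the rules.

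**Inputs.** TEAE window: 30 days after last dose (SAP 8.2.1). Safety visit: 30 to 35 days after its anchor, which is EOT in Protocol 6.4.1 and Tables 4 and 5, and last dose in the synopsis. Lag *x* from last dose to EOT: not fixed anywhere, so assumed. Fourteen days is the interruption length in Protocol 5.4.2 and Table 2. Twenty-one days is the threshold in Protocol 5.4.5, which can be exceeded. Eight days is a subject on the intermittent schedule whose last dose is Day 14 and who stops at the next Day 1 (Day 22): 22 − 14 = 8.

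**Formulas (EOT anchor).** Visit day after last dose = 30 + *x* to 35 + *x*. Uncovered days up to the visit = visit day − 30 = *x* to *x* + 5. Uncovered share of the post-dose span = uncovered days ÷ visit day.

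| Assumed lag *x* | Visit day after last dose | Uncovered days | Share of post-dose span |
|---|---|---|---|
| 0 | 30–35 | 0–5 | 0–14% |
| 7 | 37–42 | 7–12 | 19–29% |
| 8 | 38–43 | 8–13 | 21–30% |
| 14 | 44–49 | 14–19 | 32–39% |
| 21 | 51–56 | 21–26 | 41–46% |

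Under the synopsis anchor the first row applies to every subject, whatever the lag.

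**Tracing three events by onset date.**
1. *A suspected-related SAE starting on day 40.* Protocol 8.3.2 requires a report. Since 40 > 30, it is not a TEAE under the SAP. The onset is known, so the default-to-TEAE rule does not rescue it. It appears in Listings 2.7.1, 2.7.2 and 2.7.5 and in none of the SAP 8.2.3 summaries. Under Protocol 9.4.2.1 it would be a TEAE.
2. *A Grade 2 event starting on day 20 that worsens to Grade 4 on day 40.* Protocol 8.1.2 and SAP 8.2.1 record each severity change as a separate AE. The first record is a TEAE and the second is not, so the maximum-severity table shows Grade 2.
3. *An unrelated SAE on day 40 with the safety visit on day 44.* The first SAE sentence of Protocol 8.3.2 makes it reportable because it precedes the last visit. The second does not, because it is past day 30 and not suspected. The two sentences conflict.

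**Onset or report date.** The phrase common to both TEAE definitions, about an event being reported for the first time, could be read as referring to the report date. SAP 8.2.1 requires missing onset dates to be queried, which points to onset, but it never says so outright.

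**The case against.** The case for leaving the window alone has substance. Thirty days after last dose is not arbitrary: Protocol 8.1.2 makes it the minimum period for monitoring new AEs, and Protocol 8.3.2 uses it as the causality threshold for SAEs. A window fixed to last dose gives every subject the same nominal post-dose period, whereas one running to the safety visit would vary with the EOT lag. These arguments stand against simply extending the window for all events. They do not explain why related events should be dropped or why the departure is unlogged.

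A reader might also infer stronger conclusions that the documents do not support:
- *Everything found at the safety visit is lost.* On an onset reading, an event found on day 35 that began by day 30 remains a TEAE, and doubtful dates default to TEAE.
- *All safety tables are affected.* Laboratory, vital sign and ECG summaries (SAP 8.3 to 8.5) are not defined by this window, and Listings 2.7.1 to 2.7.5 keep late AEs.
- *The tables are biased downward for subjects who stop for toxicity.* The toxicity behind a hold starts on treatment and is counted, as is anything starting in the next 30 days. The uncovered span can be longer in these subjects under the EOT anchor, but no loss of events is shown.
- *Calciphylaxis and keratitis illustrate the loss.* Protocol 1.3.2 reports both as TEAEs leading to discontinuation, so they were captured. The animal findings in Protocol 1.3.1 are described as irreversible, which is not the same as late in onset. The scheduled eye examination is at EOT, not at the safety visit.

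**Conclusion.** The SAP narrows the Protocol's TEAE definition without declaring it, and AEs with a known onset or worsening after day 30, related ones included, reach the listings but no AE summary table. Up to the safety visit the uncovered span is 0 to 5 days under the synopsis anchor, or when EOT falls on the last-dose day. Under the EOT anchor it is *x* to *x* + 5 days: 14 to 19 for an assumed 14-day lag and 21 to 26 for an assumed 21-day lag. Related SAEs reported after the visit lie beyond that span as well. This rests on onset date governing and on assumed lags. The documents give no count of late events, and it may be small. It is a modest reporting gap, worth closing because closing it costs little.

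**What to change.** **In SAP 8.2.1**, state that the date of onset or worsening governs, then do one of the following:
- count any AE or SAE judged related as a TEAE regardless of time since last dose; or
- keep the 30-day window and add a summary table of treatment-related AEs, SAEs and related deaths with onset more than 30 days after last dose.

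Extending the window to the safety visit would not be enough, because related SAEs starting after that visit would still be left out.

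**In SAP 9.1**, log the departure from Protocol 9.4.2.1 with its reason.

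**In the Protocol**, reconcile the safety-visit anchor between the synopsis and Section 6.4.1 with Tables 4 and 5, and reconcile the two SAE reporting sentences in Section 8.3.2.

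The cost is a few sentences of SAP text, one programming flag or one extra table, and a Protocol clarification. Under the first option, AE rates may become slightly less favourable.

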8.2.2. Clinically Notable Adverse Events

Specific groupings of clinically notable AEs will be considered and the number of participants with at least 1 event within each grouping will be reported. Such groups consist of AEs for which there is a specific clinical interest in connection with the study drug or AEs that are similar in nature (although not identical). The groups are defined as per [Table 3](#). All clinically notable AEs are defined through reviewing PT according to the current MedDRA v21.1.

Table 3: Clinically Notable Adverse Events Groupings

Categories	Preferred Terms
Serous retinal detachment	Serous retinal detachment, detachment of macular retinal pigment epithelium, detachment of retinal pigment epithelium, retinal detachment, subretinal fluid, chorioretinopathy, retinal pigment epitheliopathy, chorioretinal disorder, retinopathy, maculopathy, retinal disorder, retinal thickening, chorioretinal folds, chorioretinal scar
Nail toxicity	Nail toxicity, nail bed tenderness, nail bed disorder, nail bed bleeding, nail disorder, nail discolouration, nail discomfort, nail dystrophy, nail hypertrophy, nail ridging, nail infection, onychalgia, onychoclasia, onycholysis, onychomadesis, onychomycosis, paronychia, fungal paronychia
Hyperphosphatemia	Hyperphosphataemia, blood phosphorus increased
Hypophosphatemia	Hypophosphataemia, blood phosphorus decreased
Dry eye	Dry eye, meibomian gland dysfunction, lacrimation increased, keratitis, punctate keratitis, pinguecula, pterygium
Eyelash changes	Eyelash changes, growth of eyelashes, trichiasis, trichomegaly
Vision blurred	vision blurred, visual impairment, visual acuity reduced
Vitreous detachment	Vitreous detachment, vitreous floaters

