Hyperphosphatemia is an expected on-target pharmacological effect of FGFR inhibition. The incidence of hyperphosphatemia, defined as any postbaseline phosphate level exceeding 5.5 mg/dL, has been observed in the majority of subjects treated with pemigatinib (refer to the [IB](#)

for complete data). Some subjects do not achieve hyperphosphatemia, and it is estimated that the pharmacological concentration of pemigatinib in these subjects is lower (see [Figure 3](#)).

Figure 3: Comparison of Steady-State Exposures for Pemigatinib 13.5 mg QD Between Subjects With Nonhyperphosphatemia and Hyperphosphatemia

AUC_{ss} = area under the curve at steady state; $C_{min,ss}$ = minimum blood plasma concentration at steady state; HP = hyperphosphatemia.

The increase in serum phosphorus observed after treatment with pemigatinib was exposure-dependent and followed a sigmoid relationship. A population E_{max} model of pemigatinib AUC and maximal serum phosphate change from baseline was developed. For those subjects treated with pemigatinib 13.5 mg who did not develop hyperphosphatemia, AUC for pemigatinib 18 mg was estimated using a linear exposure relationship. Maximal serum phosphate change from baseline for each individual was then estimated using a population model. The maximal serum phosphate after treatment with pemigatinib 18 mg was calculated by adding the baseline of serum phosphate. The simulation suggested that the serum phosphate would increase above 5.5 mg/dL after treatment with pemigatinib 18 mg for the subjects treated with pemigatinib 13.5 mg who did not develop hyperphosphatemia.

Therefore, Protocol Amendment 4 allowed up-titration of pemigatinib to increase the dose of pemigatinib in subjects who do not achieve hyperphosphatemia when treated with 13.5 mg QD. The goal is to increase the serum concentration of pemigatinib for subjects who are assumed to have lower exposure based on a lower serum phosphate level while on treatment. See [Section 5.4.4](#) for details.

Subjects will be monitored on an ongoing basis throughout this study as per the schedule of assessments (see [Table 4](#) and [Table 5](#)).

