8. SAFETY MONITORING AND REPORTING

8.1. Adverse Events

8.1.1. Definitions

For the purposes of this Protocol, an adverse event (AE) is defined as any untoward medical occurrence associated with the use of a drug in humans, whether or not considered drug related, that occurs after a subject provides informed consent.

Events meeting the AE definition include the following:

- Any safety assessments (eg, ECG, vital signs measurements), including those that worsen from baseline, considered clinically significant in the medical and scientific judgment of the investigator (ie, not related to progression of underlying disease).
- Abnormal laboratory test results constitute an AE if they are considered clinically meaningful, induce clinical signs or symptoms, require concomitant therapy, or require changes in study drug. Whenever possible, a diagnosis (eg, anemia, thrombocytopenia) should be recorded in the eCRF rather than the abnormal lab result (eg, low hemoglobin, platelet count decreased).
- Exacerbation of a chronic or intermittent pre-existing condition including either an increase in frequency and/or intensity of the condition.
- New conditions detected or diagnosed after study treatment administration even though they may have been present before the start of the study.
- Signs, symptoms, or the clinical sequelae of a suspected drug-drug interaction.
- Signs, symptoms, or the clinical sequelae of a suspected overdose of either study treatment or a concomitant medication. Overdose per se will not be reported as an AE/SAE unless it is an intentional overdose taken with possible suicidal/self-harming intent. Such overdoses should be reported regardless of sequelae.

Events not meeting the AE definition include the following:

- Any clinically significant abnormal laboratory findings or other abnormal safety assessments that are associated with the underlying disease, unless judged by the investigator to be more severe than expected for the subject's condition.
- The disease/disorder being studied or expected progression, signs, or symptoms of the disease/disorder being studied, unless more severe than expected for the subject's condition or considered to be treatment-related by the investigator.

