8.2. Laboratory Test Abnormalities

Laboratory abnormalities that constitute an AE in their own right (considered clinically meaningful, induce clinical signs or symptoms, require concomitant therapy, or require changes in study drug) should be recorded on the Adverse Event form in the eCRF. Whenever possible, a diagnosis rather than a symptom should be provided (eg, "anemia" instead of "low hemoglobin"). Laboratory abnormalities that meet the criteria for AEs should be followed until they have returned to normal or an adequate explanation of the abnormality is found. When an abnormal laboratory test result corresponds to a sign or symptom of a previously reported AE, it is not necessary to separately record the laboratory test result as an additional event.

Laboratory abnormalities that do not meet the definition of an AE should not be reported as AEs. A Grade 3 or 4 (severe) AE does not automatically indicate an SAE unless it meets the definition of serious, as defined in Section [8.3.1](#). A dose modification for the laboratory abnormality may be required (see Section [5.4](#)) and should not contribute to the designation of a laboratory test abnormality as an SAE.

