9.4.2.2. Clinical Laboratory Tests

Laboratory test values outside the normal range will be assessed for severity based on the normal ranges for the clinical reference laboratory. The incidence of abnormal laboratory values and shift tables relative to baseline will be tabulated.

Laboratory data will be classified into Grades 1 through 4 using CTCAE v4.03. The following summaries will be produced for the laboratory data:

- Number and percentage of subjects with worst postbaseline CTCAE grade (regardless of baseline value). Each subject will be counted only for the worst grade observed postbaseline.
- Shift tables from baseline to the worst postbaseline value using CTCAE grade.
- For laboratory parameters where CTCAE grades are not defined, shift tables to the worst postbaseline value using the low/normal/high classifications based on laboratory reference ranges.

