8.3.2. Laboratory Value Summaries

All test results and associated normal ranges will be converted to SI units. All tests with numeric values will have a unique unit per test.

Numeric laboratory values will be summarized descriptively in SI units, and non-numeric test values will be tabulated when necessary. In addition, line graph will be provided for phosphate, creatinine, blood urea nitrogen, calcium, sodium, 1,25-dihydroxyvitamin D, 25-hydroxyvitamin D, and parathyroid hormone.

Severity grades will be assigned to laboratory test values based on the numeric component of CTCAE v4.03. Shift tables will be presented showing change in CTCAE grade from baseline to worst grade postbaseline. Separate summaries for abnormally high and abnormally low laboratory values will be provided when the laboratory parameter has both high and low grading criteria. The denominator for the percentage calculation will be the number of participants in the baseline category. The number of participants who experienced worsening of laboratory abnormalities will be summarized by maximum severity.

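### The SAP counts hyperphosphatemia only from adverse event terms, so no planned table gives its incidence by measured phosphate; separately, a Protocol laboratory shift table is missing from the SAP and its removal is not declared.

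*SAP*

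**What the plan says.** **Adverse event route.** SAP 8.2.2 sets up a hyperphosphatemia category made of the terms "Hyperphosphataemia, blood phosphorus increased", and states the general rule: "All clinically notable AEs are defined through reviewing PT according to the current MedDRA v21.1". The clinically notable event tables in SAP 8.2.3 and Appendix C (3.2.17 to 3.2.22) follow from that. Protocol 9.4.2.1, in its adverse events section, says "The number and percentage of subjects with at least 1 event of HP will be tabulated" and does not say whether an event is a report or a laboratory value.

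**Laboratory definition.** Protocol 1.3.2.1 describes hyperphosphatemia as "defined as any postbaseline phosphate level exceeding 5.5 mg/dL". Protocol 5.4.4 uses the same cut-off for up-titration, and Protocol 5.4.3 (Protocol Table 3) sets management bands at 5.5, 7 and 10 mg/dL.

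**When a laboratory value is an adverse event.** Protocol 8.1.1: "Abnormal laboratory test results constitute an AE if they are considered clinically meaningful", or if they cause signs or symptoms, need concomitant therapy, or need a study drug change. Protocol 8.2 adds: "Laboratory abnormalities that do not meet the definition of an AE should not be reported as AEs".

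**Laboratory shift tables.** Protocol 9.4.2.2 plans, besides the CTCAE tables, the following: "For laboratory parameters where CTCAE grades are not defined, shift tables to the worst postbaseline value", classed as low, normal or high. SAP 8.3.2 has only: "Shift tables will be presented showing change in CTCAE grade from baseline to worst grade postbaseline". SAP 9.1 declares one departure from the Protocol, in the efficacy evaluable population.

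**The concern.** Hyperphosphatemia is the expected on-target effect of the drug and the most frequent treatment-emergent event in the Protocol's own safety summary. The trial acts on a measured value but reports a rate that depends on whether the investigator recorded an event. Those can differ, and the difference can vary by site.

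Two things are at stake. The first is the incidence figure for the best-known toxicity. The second is the description of who did not reach 5.5 mg/dL, since that is the group considered for 18 mg. Participants without a hyperphosphatemia adverse event are not necessarily that group.

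The missing shift tables are a separate matter of consistency between Protocol and SAP.

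**Working it through.** **1. Where the two definitions can part.** Set Protocol Table 3 against the adverse event rule in Protocol 8.1.1.

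| Phosphate (mg/dL) | Protocol Table 3 | Does it meet the adverse event rule? |
|---|---|---|
| >5.5 to 7 | Low-phosphate diet; no action on study drug | Not necessarily. Whether diet counts as concomitant therapy is not stated |
| >7 to 10 | Phosphate binder; interruption if it persists or recurs | Yes, if managed as described |
| >10 | Binder adjusted, phosphaturic agent; interruption if it persists for 1 week | Yes, if managed as described |

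The exposure is therefore mainly in the lowest band.

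**2. What the SAP does with measured phosphate.**
- By-visit values and change from baseline (SAP 8.3.1; Table 3.3.1.2), with minimum and maximum (SAP 5.1).
- A line graph (SAP 8.3.2).
- Worsening of laboratory abnormalities by maximum severity (Table 3.3.3.5).
- Listings of all and of abnormal chemistry values (2.8.2, 2.8.6).
- The number (%) on phosphate binders (SAP 6.6).

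None of these is a count of participants by worst phosphate against 5.5, 7 or 10 mg/dL. By-visit summaries cannot stand in for one:
- SAP 4.1.6 uses nominal visits without windowing, while the Protocol asks for phosphate at least twice weekly once it is above 7 mg/dL. A peak between visits need not appear.
- After Cycle 1 (Days 1, 8 and 15), scheduled visits fall on Day 1 only. On the intermittent schedule Day 1 follows a 7-day break: 7 × 24 = 168 h, and with a half-life of 18.8 h (Protocol 1.3.2.1), 168 / 18.8 = 8.9 half-lives. The documents do not say how fast phosphate falls off drug, but these samples are taken when drug exposure is lowest. This does not apply to continuous dosing.

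**3. The stated figures, reproduced.**
- Pooled monotherapy, adverse event (Protocol 1.3.2): 448/732 = 61.2%; intermittent 230/438 = 52.5%; continuous 218/294 = 74.1%.
- This study, adverse event (Protocol 1.3.2, as of 16 APR 2023): 35/47 = 74.5%, Clopper-Pearson 95% CI 59.7% to 86.1%.
- Study 101 at 13.5 mg, by phosphate threshold (Protocol 1.1.1): 83.8%, with no denominator given. The unit is printed there as mg/mL, against mg/dL elsewhere.

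**4. How large could the difference be?** The documents give no count of participants in this study above 5.5 mg/dL. Assume that all 35 with the event exceeded it, and that k of the other 47 − 35 = 12 did too. The laboratory-based rate is (35 + k)/47:

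| k | 0 | 2 | 4 | 6 | 12 |
|---|---|---|---|---|---|
| Rate | 74.5% | 78.7% | 83.0% | 87.2% | 100% |

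Nothing in the documents picks a value of k. The adverse event terms carry no threshold, so the assumption about the 35 is also unverified.

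**5. The shift tables.** Appendix C lists chemistry shifts in CTC grade only (Table 3.3.3.2). The SAP is based on Protocol Amendment 5, and the Protocol under review is Amendment 6. The Amendment 6 summary of changes names no change to Section 9.4.2.2, so a version difference is an unlikely explanation.

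Whether the omission touches phosphate depends on whether CTCAE v4.03 grades high phosphate, which the documents do not say. If it does not, no worst-value phosphate table remains. If it does, Table 3.3.3.2 gives a worst-value shift, but nothing ties its grades to the Protocol's bands.

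**The case against.** The best defence is that the SAP follows the Protocol. The Protocol's own hyperphosphatemia count sits under adverse events, and neither document ever planned a table by 5.5, 7 and 10 mg/dL. That stands: the threshold table is an improvement, not the repair of a deviation. Only the missing low/normal/high shifts depart from the Protocol.

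It is also fair that the adverse event route should capture values treated with binders or a drug change, that investigators may report lower values as well, and that the maximum per visit is shown. This narrows the gap to the lowest band and to participant-level incidence. It does not close it.

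Up-titration uses measured phosphate during the trial, so the SAP's count cannot change who receives 18 mg. The primary endpoint is untouched. Both points are right and limit the weight of the matter to safety reporting.

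Finally, restoring the Protocol's shift tables would not supply the 5.5 mg/dL incidence, because they use laboratory reference ranges. That is correct, and it is why the two repairs are kept apart.

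**Conclusion.** Followed as written, the SAP produces no incidence of hyperphosphatemia on the definition that the Protocol states and acts on. Reported events may miss participants whose phosphate stayed between 5.5 and 7 mg/dL, and reporting may differ between sites. Separately, Protocol-planned shift tables for ungraded parameters are absent from SAP 8.3.2 and Appendix C without being declared in SAP 9.1. Both are descriptive safety matters.

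A reader might infer that hyperphosphatemia will be undercounted by 9 to 23 points (83.8 − 74.5 = 9.3; 83.8 − 61.2 = 22.6). The documents do not support that. The three rates come from different populations, and the pooled figure includes Study 101, whose doses ran from 1 to 20 mg. The interval for 35/47 (59.7% to 86.1%) contains 83.8%. These rates should not be compared, and the size of any undercount is unknown.

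A reader might also infer that measured phosphate is ignored, or that the missing shift tables cause the phosphate gap. The first is wrong, since phosphate is summarized, graphed and listed. The second rests on an assumption about CTCAE v4.03 that needs checking.

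**What to change.** Keep the adverse event count and make two additions to SAP 8.3.2 and Appendix C.

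1. A table of the number (%) of participants in the safety population by worst postbaseline phosphate: >5.5 to 7, >7 to 10 and >10 mg/dL, with the total above 5.5 mg/dL. Use scheduled and unscheduled local laboratory values. SAP 8.3.2 converts results to SI units, so state the bands in those units too. The bands are the Protocol's own, and no clinical rule changes.
2. The low/normal/high shift tables to the worst postbaseline value for parameters without CTCAE grades, as Protocol 9.4.2.2 plans. If the sponsor decides against them, declare the removal in SAP 9.1. State in the SAP whether high phosphate is treated as graded.

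The cost is two or three extra descriptive tables. Chemistry is run at each site's local laboratory, so reference ranges differ by site, but the data are already collected and SAP 8.3.2 already converts results and ranges to SI units. No new sampling is needed and the primary analysis is not affected.
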